### 6.3 Withdrawal criteria

Subjects are free to withdraw from the study at any time, without prejudice to their continued care.

Subjects should be withdrawn from the study and encouraged to come for the SFU visit (20 weeks after the last received dose) if any of the following events occur:

1. Subject withdraws his/her consent.
2. The Sponsor or a regulatory agency requests withdrawal of the subject.

Subjects should be withdrawn from all study treatment and will be asked to return for the study assessments 12 weeks after the first dose (ie, the Week 12 Visit) and for the SFU Visit (20 weeks after the last received dose) if any of the following events occur:

1. There is confirmation of a pregnancy during the study, as evidenced by a positive pregnancy test.
- 2a. Subject develops an illness that in the opinion of the Investigator would interfere with his/her continued participation if the risk of continuing participation outweighs the potential benefit.
- 3a. Subject develops erythrodermic, guttate, or pustular form of psoriasis.
4. Subject considered as having either a suspected new LTb infection or who develop active TB or nontuberculosis mycobacterium (NTMB) infection during the study (including but not

limited to, conversion demonstrated by interferon-gamma release assay [IGRA] or other diagnostic means) must be immediately discontinued from study medication, an Early Withdrawal Visit must be scheduled as soon as possible, but not later than the next regular visit.

Confirmed active TB is a serious adverse event (SAE) and must be captured on an SAE Report Form and provided to the Sponsor in accordance with SAE reporting requirements. As with all SAEs, periodic follow-up reports should be completed as per protocol requirements until such time as the TB infection resolves.

Additional information on TB policies are provided in [Section 12.6.1](#).

5. Subject is noncompliant with the study procedures or medications in the opinion of the Investigator.
6. Subject uses prohibited concomitant medications, with the exception of topicals, as defined in this protocol ([Section 7.8.2](#)), that may present a risk to the safety of the subject in the opinion of the Investigator and/or the Medical Monitor.
8. Subject has active suicidal ideation as indicated by a positive response (“Yes”) to questions 4 or 5 or to the suicidal behavior questions of the “Since Last Visit” version of the self-rated electronic Columbia Suicide Severity Rating Scale (eC-SSRS). The subject should be referred immediately to a Mental Healthcare Professional and must be withdrawn from the study.
- 9a. Subjects with a HADS-D score  $\geq 15$  must be withdrawn. Any subject who develops a HADS-D score of  $>10$  during the study should be referred immediately to a Mental Healthcare Professional for further evaluation and potential withdrawal by the Investigator.
10. Subject experiences an AE as described below:
  - Any Common Terminology Criteria for Adverse Events (CTCAE) Grade 3 and above AE that is assessed as related to study drug in the opinion of the Investigator
    - If the event is deemed to be not related to study drug by the Investigator, the subject may remain in the study after approval by the medical monitor.
  - Any CTCAE Grade 2 event that is evaluated as related to study drug in the opinion of the Investigator, is persistent, and falls into any of the following System Organ Classes (SOCs): “Blood and lymphatic disorders,” “Cardiac disorders,” or “Vascular disorders.”
    - Persistent is defined as lasting 28 days or more, which spans at least 2 scheduled injections.
11. Subject has a clinical laboratory value meeting the following criteria:
  - CTCAE Grade 3 and above: subjects must be withdrawn regardless of relationship to study drug or duration of event.
  - CTCAE Grade 2
    - Subjects may remain in the study if the event is transient. If a subject has a Grade 2 laboratory abnormality, a retest is required within 1 to 2 weeks at a scheduled or unscheduled visit. If the repeat value is below Grade 2, the subject may receive the

next scheduled study treatment. If the value on the repeat is still Grade 2 or above, a second repeat test must be performed and results made available prior to the next scheduled study treatment. If this second repeat value is still Grade 2 or above, the subject must be withdrawn.

Investigators should attempt to obtain information on subjects in the case of withdrawal or discontinuation. For subjects considered as lost to follow-up, the Investigator should make an effort (at least 1 phone call and 1 written message to the subject), and document his/her effort (date and summary of the phone call and copy of the written message in the source documents), to complete the final evaluation. All results of these evaluations and observations, together with a narrative description of the reason(s) for removing the subject, must be recorded in the source documents. The Case Report Form (CRF) must document the primary reason for withdrawal or discontinuation.

Investigators should contact the Medical Monitor, whenever possible, to discuss the withdrawal of a subject in advance.

### 6.3.1 Potential drug-induced liver injury IMP discontinuation criteria

Subjects with potential drug-induced liver injury (PDILI) must be assessed to determine if IMP must be discontinued. In addition, all concomitant medications and herbal supplements that are not medically necessary should also be discontinued.

The PDILI criteria below require immediate and permanent discontinuation of IMP:

- Subjects with either of the following:
  - ALT or AST  $\geq 5xULN$
  - ALT or AST  $\geq 3xULN$  and coexisting total bilirubin  $\geq 2xULN$
- Subjects with ALT or AST  $\geq 3xULN$  who exhibit temporally associated symptoms of hepatitis or hypersensitivity. Hepatitis symptoms include fatigue, nausea, vomiting, right upper quadrant pain or tenderness. Hypersensitivity symptoms include fever (without clear alternative cause), rash, or eosinophilia (ie,  $>5\%$ ).

The PDILI criterion below allows for subjects to continue on IMP at the discretion of the Investigator.

- Subjects with ALT or AST  $\geq 3xULN$  (and  $\geq 2x$  baseline) and  $< 5xULN$ , total bilirubin  $< 2xULN$ , and no eosinophilia (ie,  $\leq 5\%$ ), with no fever, rash, or symptoms of hepatitis (eg, fatigue, nausea, vomiting, right upper quadrant pain or tenderness).

Evaluation of PDILI must be initiated as described in [Section 12.5.1](#). If subjects are unable to comply with the applicable monitoring schedule, IMP must be discontinued immediately.

Investigators should attempt to obtain information on subjects in the case of IMP discontinuation to complete the final evaluation. Subjects with PDILI should not be withdrawn from the study until investigation and monitoring are complete. All results of these evaluations and observations, as well as the reason(s) for IMP discontinuation and subject withdrawal (if applicable), must be recorded in the source documents. The CRF must document the primary reason for IMP discontinuation.

## **7 STUDY TREATMENT(S)**

### **7.1 Description of investigational medicinal product(s)**

The investigational medicinal products (IMPs) used in this study are bimekizumab and placebo.

Bimekizumab will be supplied as a clear to opalescent, colorless to slightly brown, sterile, preservative free solution in 2mL Type I, colorless glass vials (1.0mL extractable volume) closed with a rubber stopper and sealed with an aluminum cap overseal. [REDACTED]

Placebo will be supplied as 0.9% sodium chloride aqueous solution (physiological saline, preservative free) of pharmacopoeia (USP/Ph.Eur) quality appropriate for injection.

Further details of the study medications and their specifications are provided in the IMP Handling Manual.

### **7.2 Treatments to be administered**

The study medication is to be administered in the clinic by study site staff as 3 sc injections. Suitable areas for sc injections are the lateral abdominal wall and upper outer thigh. During each dosing visit, each of the 3 injections should be administered at a separate injection site. Injection sites should be rotated and injections should not be given into areas where the skin is tender, bruised, red or hard. The injection should last approximately 20 seconds.

Study medication will be administered at Baseline, Week 4, and Week 8. Study medication will also be administered at Week 12 for all subjects entering the extension study. The minimum of time between doses should be no less than 24 days and no more than 32 days.

An IMP Handling Manual will be provided to each site containing instructions regarding drug preparation and dosing.

### **7.3 Packaging**

Bimekizumab and placebo will be packaged and labeled according to Good Manufacturing Practice (GMP) guidelines and applicable laws or regulations. They will be suitably packaged in such a way as to protect the product from deterioration during transport and storage. Further information regarding storage and transport conditions are provided in the IMP Handling Manual.

### **7.4 Labeling**

Clinical drug supplies will be labeled in accordance with the current International Conference on Harmonisation (ICH) guidelines on Good Clinical Practice (GCP) and GMP and will include any locally required statements. If necessary, labels will be translated into the local language. Details on labeling will be provided in the IMP Handling Manual.

### **7.5 Handling and storage requirements**

Study drug product (IMP) must be stored under refrigerated conditions (2°C to 8°C) and protected from light. The study drug must not be frozen.

The Investigator (or designee) is responsible for the safe and proper storage of IMP at the site. Investigational medicinal product stored by the Investigator is to be kept in a secured area with limited access.

Appropriate storage conditions must be ensured by controlled temperature and by completion of a temperature log in accordance with local requirements on a regular basis per study manuals, showing minimum and maximum temperatures reached over the time interval.

Study drug will be shipped to the study sites in temperature controlled containers. Out-of-range shipping or storage conditions must be brought to the attention of the Sponsor or designee, immediately. Authorization to use any out-of-range IMP must be documented and received prior to dispensing or administering the IMP at the study site.

## **7.6 Drug accountability**

A Drug Accountability form will be used to record IMP dispensing and return information on a by-subject basis and will serve as source documentation during the course of the study. Details of any IMP lost (due to breakage or wastage), not used, disposed of at the study site, or returned to the Sponsor or designee must also be recorded on the appropriate forms. All supplies and pharmacy documentation must be made available throughout the study for UCB (or designee) to review.

In order to maintain the blind, all study drug documentation (eg, shipping receipts, drug accountability logs, IXRS randomization materials) must be maintained and accessed by unblinded, trained site personnel only. Designated, unblinded site personnel must be appropriately trained and licensed (per country guidelines) to administer injections.

Blinded study staff may be delegated the responsibility to receive, inventory, and destroy the used kits. The packaging identifies each kit by a unique number that does not correlate to the contents and therefore, does not unblind study site staff. Unblinded study staff will be responsible for preparation (breaking tamper proof sticker on kit, etc) of the clinical trial material, including recording the administration information on source document.

The Investigator (or designee) is responsible for retaining all used, unused, and partially used containers of IMP until returned or destroyed.

The Investigator may assign some of the Investigator's duties for drug accountability at the study site to an appropriate pharmacist/designee.

The Investigator must ensure that the IMP is used only in accordance with the protocol.

Periodically, and/or after completion of the clinical phase of the study, all used (including empty containers) and unused IMP containers must be reconciled and returned to UCB (or designee), preferably in their original package. Onsite destruction of used kits only may be allowed with prior approval from the Sponsor or designee after reconciliation. Investigational medicinal product intended for the study cannot be used for any other purpose than that described in this protocol.

## **7.7 Procedures for monitoring subject compliance**

During the treatment period of this study, study medication will be administered in the clinic and compliance will be determined at the visit by study personnel. Drug accountability must be recorded on the Drug Accountability Form.

## 7.8 Concomitant medication(s)/treatment(s)

All concomitant medications, including over the counter products, herbal, traditional remedies, vitamin/mineral supplements, other dietary supplements, “nutraceuticals,” and hormones must be recorded in the subject’s source documentation (eg, clinical chart) and on the electronic Case Report Form (eCRF). This record should include the name of the drug, the dose, the route and date(s) of administration, and the indication for use.

The Investigator should examine the acceptability of all concomitant procedures, medications, topical preparations and dietary supplements not explicitly prohibited in this study, and if necessary, discuss with the Medical Monitor.

In order to ensure that appropriate concomitant therapy is administered, subjects will be instructed to consult with the Investigator prior to taking any medication (either self-administered non-prescription drugs or prescription therapy prescribed by another physician).

### 7.8.1 Permitted concomitant treatments (medications and therapies)

#### Topical medications

Subjects may continue to use topical moisturizers or emollients, bath oils, or oatmeal bath preparations for skin conditions during the study, as needed. Over-the-counter shampoos for the treatment of psoriasis of the scalp are also permitted.

Subjects who use prohibited topical medications will be allowed to stay in the study but will be counseled to not use them further. No other topical preparations are allowed in the 2 weeks before randomization or during the study unless medically required to treat an AE.

#### Other medications

Subjects who are already receiving an established NSAID regimen (at least 8 weeks prior to Baseline) and have been on a stable dose for at least 4 weeks prior to Baseline may continue their use during the study. However, initiation of, or increase in dosage of, NSAIDs during the study (especially in subjects with a history of GI intolerance to NSAIDs or a history of GI ulceration) should be done with caution. Intra-articular steroid injections for arthritis of the knee are allowed.

Subjects who are already receiving an established anti-depressant regimen should be on a stable dose of anti-depressant for 12 weeks prior to Baseline.

### 7.8.2 Prohibited concomitant treatments (medications and therapies)

The list of prohibited concomitant medications is provided [Table 7-1](#).

Subjects who use prohibited medications, with the exception of topicals, will be withdrawn from study treatment but followed until the SFU.

As noted above, subjects who use prohibited topical medications will be allowed to stay in the study but will be counseled to not take them further.

**Table 7–1: Prohibited psoriasis medications**

Drug	Exclusion criteria relative to Baseline Visit
Systemic retinoids	12 weeks
Systemic treatment (non-biological): systemic immunosuppressant agents (eg, methotrexate, cyclosporine, azathioprine, thioguanine) systemic fumarate systemic corticosteroids phototherapy or chemophototherapy	8 weeks for methotrexate, azathioprine, and cyclosporine 4 weeks for everything other than methotrexate, azathioprine, and cyclosporine
Anti-TNFs: infliximab (including biosimilar), golimumab etanercept (including biosimilar) certolizumab pegol adalimumab (including biosimilar)	4 weeks for etanercept 12 weeks for everything other than etanercept
Other biologics and other systemic therapies: apremilast ustekinumab	12 weeks for apremilast 24 weeks for ustekinumab
Anti-IL-17 therapy:	Any previous exposure excluded
Any other antipsoriatic agent (systemic) under investigation (or approved after the protocol is approved)	24 weeks
Topical corticosteroids for dermatological use Vitamin D analogues and topical retinoids Keratolytic and coal tar	2 weeks
Any other antipsoriatic agent (topical) under investigation	4 weeks

IL-17=interleukin 17; TNF=tumor necrosis factor

Subjects who take prohibited medications, except topical therapies, may be withdrawn from study treatment but followed until the Safety Follow-Up. The decision to withdraw a subject for taking prohibited medications should be made in consultation with the Medical Monitor. As noted above, subjects that use prohibited topical medications will be allowed to stay in the study but will be counseled to not use them further.

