The pairwise comparisons of bimekizumab versus placebo will be formally evaluated for statistical significance only if the primary dose response efficacy analysis is statistically significant. Once the dose response has been established, pairwise testing of each bimekizumab dose versus placebo will account for multiplicity by using a fixed sequence testing procedure with each bimekizumab dose being tested sequentially from the highest dose to the lowest dose. Each test will only be conducted if the previous test reaches significance at a 2-sided significance level of  $\alpha=0.05$ . This procedure will control the overall Type I error rate. A pairwise comparison will also be made for the bimekizumab 160mg Q4W group versus the bimekizumab 320mg loading dose followed by bimekizumab 160mg Q4W group, but this evaluation will not be part of the sequential testing procedure described above (ie, the p-value will be nominal).

Non-responder imputation (NRI) will be used to account for missing data in the primary analysis. That is, subjects with a missing PASI score at Week 12 or who discontinued study treatment prior to the Week 12 Visit will be considered non-responders for the primary analysis.

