7 MEASUREMENTS OF TREATMENT COMPLICANCE

Due to the method of administration of the treatments, compliance will be examined in terms of completed doses, where one dose will be considered as one complete treatment administration (ie, three injections).

Treatment compliance will be calculated as:

total number of completed doses
$$total number of expected doses$$
 $total number of expected doses$ $total number of expected doses$

where the total number of expected doses is derived relative to when the subject finishes treatment. If a subject completes treatment nine doses are expected (three each at Baseline, Week 4 and Week 8). If a subject discontinues early, then the number of expected injections is based on the time of early discontinuation relative to the dosing visits.

A summary of percent treatment compliance categorized as ≤75% and >75% will be provided by treatment group.

A by-subject listing of treatment compliance will be provided.

EFFICACY ANALYSES 8

Statistical analysis of the primary efficacy variable 8.1

Derivations of PASI score and response 8.1.1

PASI scoring of psoriatic plaques is based on three criteria: redness (R), thickness (T), and scaliness (S). Severity is rated for each index (R, S, T) on a 0-4 scale (0 for no involvement up to 4 for very marked involvement). The body is divided into four areas comprising the head (h), upper extremities (u), trunk (t), and lower extremities (l). In each of these areas, the fraction of total surface area affected is graded on a 0-6 scale (0 for no involvement; up to 6 for 90% - 100% involvement).

The various body regions are weighted to reflect their respective proportion of BSA. The composite PASI score is then calculated by multiplying the sum of the individual-severity scores for each area by the weighted area-of-involvement score for that respective area, and then summing the four resulting quantities as follows (note for R, T, and S scores are as follows: 0 = none, 1 = slight, 2 = moderate, 3 = marked, and 4 = very marked):

$$PASI = (0.1 \times (R_h + T_h + S_h) \times A_h) + (0.2 \times (R_u + T_u + S_u) \times A_u) + (0.3 \times (R_t + T_t + S_t) \times A_t) + (0.4 \times (R_l + T_l + S_l) \times A_l)$$
(4)

where

 R_h , R_u , R_t , R_l = redness score of plagues on the head, upper extremities, trunk, and lower extremities, scored 0-4 respectively;

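### Protocol 7.8.2 leaves withdrawal for prohibited systemic psoriasis therapy both mandatory and discretionary, and non-responder imputation does not cover such therapy, so a subject kept on study drug while using it can count as a PASI90 responder

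*Protocol*

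**What the plan says.** **Withdrawal rule.** Three current passages of the protocol deal with the same event.

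- Section 7.8.2, before Table 7-1: "Subjects who use prohibited medications, with the exception of topicals, will be withdrawn from study treatment but followed until the SFU".
- Section 7.8.2, under Table 7-1: such subjects "may be withdrawn from study treatment but followed until the Safety Follow-Up", and "The decision to withdraw a subject for taking prohibited medications should be made in consultation with the Medical Monitor".
- Section 6.3 item 6 lists prohibited non-topical use as a reason to stop study treatment, but qualifies it as use "that may present a risk to the safety of the subject in the opinion of the Investigator and/or the Medical Monitor". Item 5 of the same list (noncompliance in the Investigator's opinion) is a further discretionary route.

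**Response and NRI.** SAP 8.1.1 derives PASI90 from the percentage change in PASI alone. Protocol 14.3.1 states that "subjects with a missing PASI score at Week 12 or who discontinued study treatment prior to the Week 12 Visit will be considered non-responders". SAP 4.2.1 and 8.1.2 repeat these two triggers, and SAP 4.2.3 applies the same pair to the other categorical efficacy variables. Neither document makes use of prohibited therapy a trigger.

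**Dosing.** Protocol 7.2: "Study medication will be administered at Baseline, Week 4, and Week 8". No PS0010 dose remains between Week 8 and the Week 12 assessment.

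**The concern.** Two sites that both follow Section 7.8.2 could treat the same subject differently. One stops study drug, so NRI makes the subject a non-responder. The other keeps the subject on study drug after consulting the Medical Monitor, so the Week 12 PASI is used as observed. Responder status then turns on a discretionary decision, and improvement produced by another agent is credited to the assigned arm.

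The plan recognises this kind of confounding elsewhere. In Protocol 14.6 and SAP 8.1.4.1 it warns that placebo subjects who withdraw may be on another active drug at Week 12. That warning concerns only withdrawn subjects in one sensitivity analysis. The retained user in the primary analysis is not addressed.

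At stake are the placebo response rate, the odds ratios of each dose versus placebo, and the secondary PASI and IGA responder endpoints. Use in the placebo arm shrinks the apparent effect; use in an active arm inflates it.

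**Working it through.** **1. Which users does NRI reach?** Take a subject with an observed Week 12 PASI improvement of at least 90% who used a Table 7-1 systemic therapy or phototherapy.

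| Case | Trigger met? | PASI90 status |
|---|---|---|
| Study drug stopped and recorded before Week 12 | Yes | Non-responder |
| Kept on study drug under the discretionary rule | No | Responder |
| Started after the Week 8 dose, withdrawal recorded before Week 12 | Plausibly yes | Non-responder on that reading |
| Started after the Week 8 dose, no withdrawal recorded | No | Responder |

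**2. Do the sensitivity analyses catch the retained user?** The all-available-data analysis and the on-treatment observed-case analysis both use the observed value. Multiple imputation has nothing to impute. Only the Per-Protocol Set might drop the subject, and Protocol 14.5 and SAP 3.4 place its deviation criteria in another document.

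**3. Primary trend test.** Inputs from Protocol 14.8 and 14.3.1: n = 40 per arm; PASI90 rates 2%, 20%, 40%, 50%, 60%; scores x = -2 to 2; two-sided 5%. Power = Φ((U - 1.96·s0)/s1).

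- U = 40 × (-0.04 - 0.20 + 0 + 0.50 + 1.20) = 58.4
- s0 = √(40 × 0.344 × 0.656 × 10) = 9.50, where 0.344 is the mean rate
- s1 = √(40 × Σx²p(1-p)) = √(40 × 1.4484) = 7.61
- Power = Φ((58.4 - 18.62)/7.61) = Φ(5.23), above 99.99%

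This agrees with the stated figure of more than 99%. With four extra placebo responders the placebo rate is (0.8 + 4)/40 = 12%. Then U = 50.4, s0 = 9.62, s1 = 8.47, and power = Φ(3.72), about 99.99%. This is the test used for sizing, not the planned logistic contrast.

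**4. Odds ratios, per user.** The documents give no number of retained users, so this is an illustration. Assumption: a user who would otherwise not respond reaches PASI90 with probability r between 0.20 and 0.592. The top is the highest Week 12 secukinumab rate cited in Protocol 14.8. It is generous for therapy started mid-study, since Table 7-1 consists mostly of other drug classes. The lower value has no source. At r = 0 nothing changes.

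One user in an arm with planned rate p gives p' = p + r(1 - p)/40.

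- Placebo: 0.02 + 0.0245r = 2.49% to 3.45%
- 64 mg: 0.20 + 0.02r = 20.4% to 21.2%

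| One user in | 64 mg odds ratio versus placebo (planned 12.25) |
|---|---|
| Placebo only | 9.79 to 7.00 |
| Both arms | 10.04 to 7.52 |
| 64 mg only | 12.56 to 13.17 |

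For 480 mg versus placebo, one placebo user moves the odds ratio from 73.5 to between 58.7 and 42.0.

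Chance alone also moves these ratios. At 2% of 40, the probability of no placebo responder is 0.98^40 = 44.6%, and of two or more it is 19.0%.

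**5. Power of 64 mg versus placebo.** Exact enumeration with one placebo user, unadjusted:

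- Pearson chi-square: 83.1% falls to between 79.0% and 71.1%.
- Wald test on the log odds ratio, counting tables with no placebo responder as non-significant: 27.4% rises to between 30.8% and 37.5%.

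The sign depends on the test, and neither document names the statistic.

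**The case against.** **The expected path already triggers NRI.** SAP 8.1.4.3 expects investigators to stop study treatment for non-responders before giving alternative therapy. Protocol 7.8 tells subjects to consult the Investigator before taking any medication, the trial is double-blind, and per-protocol exclusions are settled before unblinding. This stands, and it is why numbers are probably small. It does not remove the discretionary rule or add the missing trigger.

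**The endpoint as written is not breached.** A reader might infer that a retained user violates the composite justified in SAP 4.2. It does not: that section names two components, clinical response and completing 12 weeks of study treatment, and a retained responder meets both. Freedom from other therapy would be an added component, to be chosen openly.

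**Starting after Week 8.** A reader might infer that such a subject has completed treatment and must be scored as observed, because SAP 7 says "If a subject completes treatment nine doses are expected (three each at Baseline, Week 4 and Week 8". That sentence runs one way only: it gives the expected count for someone who completes and does not define completion by the count. SAP 3.9.2 runs the treatment period to the Week 12/WD visit, and SAP 10.1.1 credits 28 days of exposure to the last injection, cut off at the Week 12 visit. A withdrawal recorded at Week 9 or 10 could therefore trigger NRI. The documents do not settle it.

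**The affected comparisons carry less weight.** Protocol 14.3.1 calls the pairwise tests supportive, Protocol 14.8 claims no power for them, and SAP 8.2 makes secondary p-values nominal. This stands and lowers the priority.

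**Conclusion.** The gap is real. On the current text a subject kept on study drug while using a Table 7-1 systemic therapy or phototherapy meets neither NRI trigger and can be a PASI90 responder. For a start after the Week 8 dose, the result depends on the site's record.

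The size is limited and cannot be estimated, because no frequency is given. Per user, the shift in the 64 mg odds ratio is that shown above, under the assumed r of 0.20 to 0.592. Direction depends on the arm.

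Two stronger readings are not supported. The primary dose-response test is not threatened: its sizing power stays at about 99.99% even at a 12% placebo rate. Nor should a loss of power for 64 mg be claimed, since the sign changes between Pearson and Wald. Low to moderate priority.

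**What to change.** **SAP 4.2.1, 8.1.2 and 4.2.3.** State that use of a Table 7-1 systemic therapy or phototherapy for psoriasis, after first dose and before the PASI or IGA assessment being analysed, counts as non-response whether or not study treatment was stopped. Make the classification from the concomitant-treatment record before unblinding.

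**Protocol 7.8.2 and 6.3 item 6.** Use one consistent withdrawal rule. Medical Monitor discretion may stay, because responder status would no longer depend on it.

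Limiting the trigger to use for psoriasis leaves a corticosteroid course for an unrelated adverse event outside it. No timed exception is needed, and Table 7-1 would not supply one: its "4 weeks for everything other than methotrexate, azathioprine, and cyclosporine" is an interval before Baseline, not an on-study rule.

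**Cost.** SAP text in three sections, two protocol wording edits (with the approvals in Protocol 15.5 if classed as significant), and one derivation flag. Protocol 7.8 already requires drug, dates and indication to be recorded; capture of phototherapy needs confirming. No new visits or subjects. The downside is that a few active-arm subjects may become non-responders.
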